### 3.4.2.7 Lipoprotein profile and free fatty acids

Lipoprotein profile including Total Cholesterol, HDL-C, LDL-C, Triglycerides, and free fatty acids will be measured at Screening, Baseline (Day 1), Week 1, Week 4, Week 8, Week 12, Week 16 and Week 20 Safety follow-up.

Non-HDL cholesterol will be calculated as Total Cholesterol - HDL-C.

ANCOVA model with treatment group as a factor and baseline value as a covariate will be used for analyzing the change from baseline and percent change from baseline to Weeks 4, 8, 12, 16, and 20. LS means, 95% confidence intervals and p-values will be presented.

#### 3.4.2.8 C3M and PRO-C3/C3M Ratio

C3M will be measured at Baseline (Day 1), Week 4, Week 8, Week 12, Week 16, and Week 20. PRO-C3/C3M Ratio will be derived at all available timepoints. ANCOVA model with treatment group as a factor and baseline value as a covariate will be used for analyzing the change from baseline to Week 12, and the change from baseline to Week 16. LS means, 95% confidence intervals and p-values will be presented.

### 3.4.2.9 Platelets

Platelets will be measured at Screening, Baseline (Day 1), Week 1, Week 4, Week 8, Week 12, Week 16 and Week 20 Safety follow-up.

ANCOVA model with treatment group as a factor and baseline value as a covariate will be used for analyzing the change from baseline and percent change from baseline to Weeks 4, 8, 12, 16, and 20. LS means, 95% confidence intervals and p-values will be presented.

3.4.2.10 Liver steatosis as evaluated by FibroScan® at Week 16 expressed in CAP

Liver steatosis will be assessed using FibroScan® at Screening and Week 16. Summary statistics at all visits for the values, change from baseline and percent change from baseline will be provided.

The change and percent change from baseline at Week 16 in liver steatosis expressed in CAP will be analyzed with an analysis of covariance (ANCOVA) model with treatment group as a factor and baseline liver steatosis as evaluated by FibroScan® as a covariate using the FAS. The treatment effect estimate, 95% CI and pvalues will be provided. Missing values at Week 16 will be imputed using the LOCF method. The same analysis will be repeated on the Liver Stiffness Evaluable Analysis Set and the PPAS, and no imputation will be performed.

### 3.4.3 Subgroups

Subgroup analyses will be performed for the secondary efficacy endpoint. The group variables include statin use, Type 2 diabetes status and baseline Endogenous FGF21.

The glycemic control biomarkers will be summarized and analyzed by the following subgroup: type 2 diabetes status.

The lipoprotein profile will be summarized and analyzed by the following subgroup: statin use.

### 3.5 Safety Assessment

The safety of EFX will be assessed during the study through the reporting of AEs, clinical laboratory tests, ECG, vital sign assessments, body weight, ADA and NAb assessments, and concomitant medication usage.

All safety data collected on or after the date that study drugs were first dispensed up to the date of last dose of study drugs plus 30 days will be summarized by treatment group. Data for the follow-up period will be included in data listings.

Safety data will be summarized by actual treatment received (and in total for selected analyses) based on the Safety Set unless otherwise specified. Selected safety data will be repeated on F4 Safety Set.

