### 3.2.2 Safety Set

The Safety Set will include all subjects who received at least one dose of study drug. The Safety Set will be the primary analysis set for safety analyses.

Subjects who received a dose of study drug other than that to which they were randomized for the entire duration of treatment will be analyzed according to the dose of study drug received. All data collected during treatment plus 30 days after last dose of study drug will be included in the safety summaries.

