### 3.3.7 Study Drug Exposure and Compliance

Weeks of exposure to study drug will be calculated as:

(date of last dose of study drug - date of first dose of study drug + 1) / 7

Weeks of exposure to study drug will be summarized by treatment based on the Safety Set with descriptive statistics and with counts and percentages of subjects with exposure in the following categories:

- >0 to ≤4 weeks
- >4 to ≤8 weeks
- >8 to ≤12 weeks
- >12 to ≤16 weeks
- >16 weeks

The total number of injections administered will be calculated for each subject. A contingency table will be provided to display the number and percentage of subjects in each treatment group with the following number of injections: 1-3, 4-6, 7-9, 10-12, 13-15, >=16.

Subjects that miss 2 or more doses of study drug over the course of study participation are considered noncompliant. The frequency and percentage of subjects who are compliant and noncompliant will be summarized by treatment group.

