### 3.5.1 Adverse Events

All AEs will be coded to system organ class and preferred term using MedDRA version 22.0 or the latest version.

Treatment-emergent adverse events (TEAEs) are defined as one or both of the following:

- Any AEs with an onset date/time on or after the study drugs start date/time and no later than 30 days after permanent discontinuation of study drugs
- Any AEs leading to premature discontinuation of study drugs.

Injection site reactions, diarrhea, hypoglycemia and drug-induced liver injuries (DILI) will be monitored as AEs of special interests (AESIs) during this study. During the course of the study, additional AESIs may be identified by the Sponsor.

An overview of AEs will be provided including counts and percentages of subjects with the following:

- Any TEAEs (overall and by maximum severity)
- Any study drug related TEAEs (overall and by maximum severity)
- Any study procedure related TEAEs (overall and by maximum severity)
- Any TEAEs of special interest (overall, injection site reactions, diarrhea, hypoglycemia, DILI)
- Any TEAE of decompensated liver disease events including ascites, hepatic encephalopathy (HE), or variceal bleeding
- Any serious AEs (SAEs)
- Any treatment-emergent serious AEs (TESAEs)

- Any TEAEs leading to premature discontinuation of study drug
- Any TEAEs leading to premature discontinuation of study
- Any AEs leading to death

Counts and percentages of subjects will also be presented by system organ class and preferred term for each of the categories in the overview, as well as the common (>=5% in any treatment group) TEAEs. Listings will be provided of all AEs, including AESIs, decompensated liver disease events, SAEs, TEAEs leading to discontinuation of study drug, and AEs leading to death. Counts and percentages of subjects will be presented by preferred term and period (weekly and every 4 weeks) for selected most frequent TEAE.

Counts and percentages of subjects will be repeated on F4 Safety Set for the following:

- An overview of AEs
- Any TEAEs (overall and by maximum severity)
- Any study drug related TEAEs (overall and by maximum severity)
- Any TEAEs leading to premature discontinuation of study drug
- Any TEAEs of special interest (overall, injection site reactions, diarrhea, hypoglycemia, DILI)

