### 3.5.2 Clinical Laboratory Tests

Chemistry, hematology, and coagulation samples will be collected at Screening, Pre-Baseline, Baseline (Day 1), Week 1, Week 4, Week 8, Week 12, Week 16 and Week 20 Safety follow-up.

All continuous laboratory parameters except of liver injury and function markers (see section 2.3.3) will be summarized descriptively by value at baseline and each planned post-baseline visit, together with the corresponding changes from baseline. All categorical laboratory parameters will be tabulated at baseline and each planned post-baseline visit.

For the selected parameters, the incidence of graded treatment-emergent laboratory abnormalities will be presented for laboratory data using the grading scheme in the Common Terminology Criteria for Adverse Events (CTCAE) Version 5.0.

Laboratory	CTCAE Term	Grade 1	Grade 2	Grade 3	Grade 4
Chemistry	Alanine aminotransferase increased	>ULN - 3.0 x ULN if baseline was normal;	>3.0 - 5.0 x ULN if baseline was normal;	>5.0 - 20.0 x ULN if baseline was normal;	>20.0 x ULN if baseline was normal;
		1.5 - 3.0 x baseline if baseline was abnormal	>3.0 - 5.0 x baseline if baseline was abnormal	>5.0 - 20.0 x baseline if baseline was abnormal	>20.0 x baseline if baseline was abnormal
	Aspartate aminotransferase increased	>ULN - 3.0 x ULN if baseline was normal;	>3.0 - 5.0 x ULN if baseline was normal;	>5.0 - 20.0 x ULN if baseline was normal;	>20.0 x ULN if baseline was normal;
		1.5 - 3.0 x baseline if baseline was abnormal	>3.0 - 5.0 x baseline if baseline was abnormal	>5.0 - 20.0 x baseline if baseline was abnormal	>20.0 x baseline if baseline was abnormal
	Blood bilirubin increased	Total Bilirubin	Total Bilirubin	Total Bilirubin	Total Bilirubin
	incroasou	>ULN - 1.5 x ULN if	>1.5 - 3.0 x ULN if	>3.0 - 10.0 x ULN if	>10.0 x ULN if
		baseline was	baseline was	baseline was	baseline was
		normal;	normal;	normal;	normal;

Laboratory	CTCAE Term	Grade 1	Grade 2	Grade 3	Grade 4
		> 1.0 - 1.5 x baseline if baseline was abnormal	>1.5 - 3.0 x baseline if baseline was abnormal	>3.0 - 10.0 x baseline if baseline was abnormal	>10.0 x baseline if baseline was abnormal
	Alkaline phosphatase increased	>ULN - 2.5 x ULN if baseline was normal;	>2.5 - 5.0 x ULN if baseline was normal;	>5.0 - 20.0 x ULN if baseline was normal;	>20.0 x ULN if baseline was normal;

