	Neutrophil count decreased	<lln -="" 1500="" mm3;
<lln -="" 1.5="" 10e9="" l<="" td="" x=""><1500 - 1000/mm3; <1.5 - 1.0 x 10e9 /L	<1000 - 500/mm3; <1.0 - 0.5 x 10e9 /L	<500/mm3; <0.5 x 10e9 /L	</lln></lln>	<1500 - 1000/mm3; <1.5 - 1.0 x 10e9 /L	<1000 - 500/mm3; <1.0 - 0.5 x 10e9 /L	<500/mm3; <0.5 x 10e9 /L
	White blood cell decreased	<lln -="" 3000="" mm3;
<lln -="" 10e9="" 3.0="" l<="" td="" x=""><3000 - 2000/mm3; <3.0 - 2.0 x 10e9 /L	<2000 - 1000/mm3; <2.0 - 1.0 x 10e9 /L	<1000/mm3; <1.0 x 10e9 /L	</lln></lln>	<3000 - 2000/mm3; <3.0 - 2.0 x 10e9 /L	<2000 - 1000/mm3; <2.0 - 1.0 x 10e9 /L	<1000/mm3; <1.0 x 10e9 /L
	Platelet count decreased	<lln -="" 75,000="" mm3;
<lln -="" 10e9
/L</lln></lln>	<75,000 - 50,000/mm3; <75.0 - 50.0 x 10e9 /L	<50,000 - 25,000/mm3; <50.0 - 25.0 x 10e9 /L	<25,000/mm3; <25.0 x 10e9 /L
Coagulation	INR increased	>1.2 - 1.5;	>1.5 - 2.5;	>2.5;	
		>1 - 1.5 x baseline if on anticoagulation	>1.5 - 2.5 x baseline if on anticoagulation	>2.5 x baseline if on anticoagulation	
		•	•	•	•

For the other parameters, the incidence of abnormalities (as defined by normal ranges) prior to the first dose of study drug and after the first dose of study drug will be summarized with counts and percentages of subjects.

The incidence of treatment-emergent laboratory abnormalities, defined as values that increase at least one toxicity grade from baseline at any time post baseline up to and including the date of last dose of study drugs plus 30 days, will be summarized with counts and percentages of subjects by treatment group. If baseline data are missing, then any graded abnormality (i.e., at least a Grade 1) will be considered treatment-emergent. If no pre-treatment laboratory value is available, the baseline value will be assumed to be normal (i.e., no grade [Grade 0]) for the summary of graded laboratory abnormalities.

Evaluation of drug-induced serious hepatotoxicity (eDISH) plot will be provided to display peak serum ALT and Total Bilirubin (TB) levels for each subject. The peak serum AST versus TB levels for each subject will also be provided.

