### 3.5.3 Vital Signs

Height will be measured without shoes at Screening. Other vital signs (body weight, BMI, systolic and diastolic blood pressure, pulse, respiration rate and oral temperature) will be measured at each visit. Triplicate blood pressure and heart rate will be measured at Baseline (Day 1) and at 48 - 96 hours post-dose on Weeks 4 and Week 8.

Values and changes from baseline to each visit and timepoint for vital signs will be summarized descriptively. Triplicate measurements will be averaged prior to summary.

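### Cohort C: with the last dose at Week 15, as the dosing row shows, the 30-day safety-summary and treatment-emergent laboratory windows nominally close on Day 136, five days before a completer's Week 20 safety visit

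*SAP*

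**What the plan says.** SAP 3.5 covers safety data from first dispensing and says that data "up to the date of last dose of study drugs plus 30 days will be summarized by treatment group". The next sentence reads: "Data for the follow-up period will be included in data listings". SAP 3.2.2 repeats the limit for the Safety Set: "All data collected during treatment plus 30 days after last dose of study drug will be included in the safety summaries". SAP 3.5.2 counts a treatment-emergent laboratory abnormality when the grade rises after baseline, "up to and including the date of last dose of study drugs plus 30 days".

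Other places point elsewhere. SAP 3.5.2 also says that continuous laboratory parameters, liver markers excepted, "will be summarized descriptively by value at baseline and each planned post-baseline visit". SAP 3.5.3 says: "Values and changes from baseline to each visit and timepoint for vital signs will be summarized descriptively". Week 20 is a planned visit with laboratory sampling and vital signs.

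The TEAE definition in SAP 3.5.1 has a different anchor: onset "no later than 30 days after permanent discontinuation of study drugs". Neither document defines permanent discontinuation.

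On the schedule, the Cohort C dosing row in protocol Appendix B is marked at Baseline and Weeks 1 to 15 and is blank at Week 16. Footnote z of that appendix places the safety follow-up four weeks after the last dose and equates this with Week 20 for completers.

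**The concern.** Safety and tolerability are the primary objective of Cohort C, and Week 20 is its scheduled safety follow-up visit. If the last dose is at Week 15, that visit comes five weeks after it, beyond a 30-day window. A new laboratory grade found there would be absent from the treatment-emergent table for a completer, whereas the same finding at an early discontinuer's follow-up would nominally be counted. Inclusion would then turn on whether the subject completed treatment.

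Separately, two programmers could build different Week 20 tables. One would follow the by-visit rule in 3.5.2 and 3.5.3; the other would follow the 30-day limit in 3.5 and only list the data.

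**Working it through.** **Inputs**
- Day convention (SAP 3.1.1): first dose is Day 1, so Week w falls on Day 7w + 1.
- Last dose (Appendix B dosing row): Week 15. Baseline plus Weeks 1 to 15 is 16 injections, in line with once-weekly dosing for 16 weeks.
- Target days (SAP 3.1.2, body-weight table): Week 15 = Day 106, Week 16 = Day 113, Week 20 = Day 141. The formula reproduces them: 7 × 15 + 1 = 106; 7 × 16 + 1 = 113; 7 × 20 + 1 = 141.
- Visit window (Appendix B footnote a): ± 3 days.
- Window close: last dose + 30 days.

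**Completer on the dosing row.** 106 + 30 = 136. The visit is 141 − 136 = 5 days past the close and 141 − 106 = 35 days after the last dose.

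**Allowing ± 3 days on both dates.** Shortest interval 138 − 109 = 29 days; longest 144 − 103 = 41 days. The visit therefore ranges from 1 day inside the window to 11 days outside. This lets the two dates move independently, which footnote z would not allow, so it is a range and not a forecast.

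**Early discontinuer.** Follow-up at 28 days is 2 days inside the window; the range is 25 to 31 days if the same ± 3 days is assumed.

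**The three schedule readings**

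| Reading | Last dose | Window closes | Visit | Position |
|---|---|---|---|---|
| Dosing row, visit at Week 20 | Day 106 | Day 136 | Day 141 | 5 days outside |
| Dosing row, visit 4 weeks after last dose | Day 106 | Day 136 | Day 134 (106 + 28) | 2 days inside |
| Last dose at Week 16, visit at Week 20 | Day 113 | Day 143 | Day 141 | 2 days inside |

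**Week 15 dose missed.** Under SAP 3.3.7, "Subjects that miss 2 or more doses of study drug over the course of study participation are considered noncompliant", so one missed dose does not make a subject noncompliant. The last dose is then Day 7 × 14 + 1 = 99 and the window closes on Day 129. A visit kept at Week 20 is 141 − 129 = 12 days outside; a visit moved to four weeks after that dose (Day 127) is 2 days inside.

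**TEAEs.** If permanent discontinuation means the last dose, an adverse event starting on Days 137 to 141 is not a TEAE. If it means the end of the 16-week period (Day 113), the limit is Day 143 and the visit is covered, but the TEAE window then runs 143 − 136 = 7 days longer than the laboratory window.

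**The case against.** The strongest reply is footnote z. Two of the three readings keep its four-week interval, and both put the visit inside 30 days. The protocol's 16 weeks on treatment plus 4 weeks of follow-up (3.2) fits it, and SAP 3.3.7 has an exposure category above 16 weeks, which a Week 15 last dose cannot reach within visit windows (109 / 7 = 15.6 weeks), although that may be only a catch-all. This stands: the five-day gap is conditional on the dosing row and the Week 20 date both prevailing.

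Second, the 30-day rule is pre-specified, repeats protocol 7.3.2, 7.7, 7.7.2 and 7.7.3, and applies to both arms. At the half-lives of 3.14 to 3.38 days in protocol 1.4.1.2, measured in diabetic subjects, 30 days is 30 / 3.38 = 8.9 to 30 / 3.14 = 9.6 half-lives. That makes 30 days a defensible definition of treatment-emergent. It does not show that leaving out Week 20 was intended, because the protocol's own footnote expects the visit at four weeks, inside the window.

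Third, much is covered elsewhere:
- All adverse events are listed, and the SAE and death rows in SAP 3.5.1 are not limited to treatment-emergent events.
- The eDISH plot states no window.
- Liver markers, including Child-Pugh (SAP 3.4.2.1), and platelets (3.4.2.9) have Week 20 analyses.
- For parameters outside the grade table, the SAP counts abnormalities after the first dose without restating the limit.
- Clinically significant laboratory values are reportable as adverse events (protocol 6.21).
- SAP 3.4.2 promises descriptive summaries of exploratory endpoints, which include decompensation.

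All of this stands and keeps the effect small. Mean changes and listings still do not replace subject-level grade incidence, and graded parameters such as creatinine, CPK, amylase and neutrophils have no Week 20 ANCOVA.

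**Conclusion.** The point holds, conditionally. On the dosing row and the SAP's target days, the safety-summary and treatment-emergent laboratory windows nominally close five days before a completer's Week 20 safety visit. Two defects remain whichever schedule reading is right: footnote z cannot be satisfied together with the dosing row, and the SAP does not say whether its by-visit rule or its 30-day rule governs Week 20 laboratory values and vital signs.

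The size is modest: newly graded laboratory values at one visit and, only if permanent discontinuation means last dose, non-serious adverse events starting in the last five days, in about 30 subjects.

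A reader might infer that Week 20 safety data are lost, that serious or decompensation events found there go unreported, or that the arms are compared unfairly. The documents do not support this. The data are collected and listed, and serious events and deaths are tabulated without the treatment-emergent restriction. Adverse events are classified by onset, so one that began by Day 136 still counts when reported at Week 20. The rule is the same in both arms, and the documents give no completion rates by arm from which a bias could be derived.

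**What to change.** 1. Reconcile the Cohort C dosing row with footnote z. No dosing or visit rule is proposed here.
2. In SAP 3.2.2, 3.5, 3.5.1 and 3.5.2, use one window anchored on the date of last dose. It ends at the later of last dose + 30 days and the scheduled safety follow-up visit, with the visit date counted no later than the upper limit of its protocol window (141 + 3 = Day 144 for completers). The cap stops a delayed visit from lengthening the window. With no follow-up visit, last dose + 30 days applies.
3. Flag onsets and laboratory values more than 30 days after the last dose, and also show the protocol's 30-day count.
4. Limit the listings-only sentence in SAP 3.5 to data after that window, so that Week 20 values are summarized as 3.5.2 and 3.5.3 require.
5. Tabulate the decompensation endpoint of SAP 2.3.2 for all events, since the only specific table, in 3.5.1, is restricted to TEAEs.
6. Record the departure from protocol 7.3.2, 7.7, 7.7.2 and 7.7.3 in SAP section 6. If the protocol text is changed as well, it also governs the Main Study and must be checked against the 30-day recording limit in 6.21.

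The cost is wording: Week 20 sampling and adverse event review are already scheduled. Under SAP section 1, a change made after unblinding would have to be documented in the CSR. The drawbacks are that a few late, off-drug events enter the main table, and that observation after the last dose still differs slightly, at about 35 days for completers against about 30 for early discontinuers.

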### 3.5.1 Adverse Events

All AEs will be coded to system organ class and preferred term using MedDRA version 22.0 or the latest version.

Treatment-emergent adverse events (TEAEs) are defined as one or both of the following:

- Any AEs with an onset date/time on or after the study drugs start date/time and no later than 30 days after permanent discontinuation of study drugs
- Any AEs leading to premature discontinuation of study drugs.

Injection site reactions, diarrhea, hypoglycemia and drug-induced liver injuries (DILI) will be monitored as AEs of special interests (AESIs) during this study. During the course of the study, additional AESIs may be identified by the Sponsor.

An overview of AEs will be provided including counts and percentages of subjects with the following:

- Any TEAEs (overall and by maximum severity)
- Any study drug related TEAEs (overall and by maximum severity)
- Any study procedure related TEAEs (overall and by maximum severity)
- Any TEAEs of special interest (overall, injection site reactions, diarrhea, hypoglycemia, DILI)
- Any TEAE of decompensated liver disease events including ascites, hepatic encephalopathy (HE), or variceal bleeding
- Any serious AEs (SAEs)
- Any treatment-emergent serious AEs (TESAEs)

- Any TEAEs leading to premature discontinuation of study drug
- Any TEAEs leading to premature discontinuation of study
- Any AEs leading to death

Counts and percentages of subjects will also be presented by system organ class and preferred term for each of the categories in the overview, as well as the common (>=5% in any treatment group) TEAEs. Listings will be provided of all AEs, including AESIs, decompensated liver disease events, SAEs, TEAEs leading to discontinuation of study drug, and AEs leading to death. Counts and percentages of subjects will be presented by preferred term and period (weekly and every 4 weeks) for selected most frequent TEAE.

Counts and percentages of subjects will be repeated on F4 Safety Set for the following:

- An overview of AEs
- Any TEAEs (overall and by maximum severity)
- Any study drug related TEAEs (overall and by maximum severity)
- Any TEAEs leading to premature discontinuation of study drug
- Any TEAEs of special interest (overall, injection site reactions, diarrhea, hypoglycemia, DILI)

### 3.5.2 Clinical Laboratory Tests

Chemistry, hematology, and coagulation samples will be collected at Screening, Pre-Baseline, Baseline (Day 1), Week 1, Week 4, Week 8, Week 12, Week 16 and Week 20 Safety follow-up.

All continuous laboratory parameters except of liver injury and function markers (see section 2.3.3) will be summarized descriptively by value at baseline and each planned post-baseline visit, together with the corresponding changes from baseline. All categorical laboratory parameters will be tabulated at baseline and each planned post-baseline visit.

For the selected parameters, the incidence of graded treatment-emergent laboratory abnormalities will be presented for laboratory data using the grading scheme in the Common Terminology Criteria for Adverse Events (CTCAE) Version 5.0.

Laboratory	CTCAE Term	Grade 1	Grade 2	Grade 3	Grade 4
Chemistry	Alanine aminotransferase increased	>ULN - 3.0 x ULN if baseline was normal;	>3.0 - 5.0 x ULN if baseline was normal;	>5.0 - 20.0 x ULN if baseline was normal;	>20.0 x ULN if baseline was normal;
		1.5 - 3.0 x baseline if baseline was abnormal	>3.0 - 5.0 x baseline if baseline was abnormal	>5.0 - 20.0 x baseline if baseline was abnormal	>20.0 x baseline if baseline was abnormal
	Aspartate aminotransferase increased	>ULN - 3.0 x ULN if baseline was normal;	>3.0 - 5.0 x ULN if baseline was normal;	>5.0 - 20.0 x ULN if baseline was normal;	>20.0 x ULN if baseline was normal;
		1.5 - 3.0 x baseline if baseline was abnormal	>3.0 - 5.0 x baseline if baseline was abnormal	>5.0 - 20.0 x baseline if baseline was abnormal	>20.0 x baseline if baseline was abnormal
	Blood bilirubin increased	Total Bilirubin	Total Bilirubin	Total Bilirubin	Total Bilirubin
	incroasou	>ULN - 1.5 x ULN if	>1.5 - 3.0 x ULN if	>3.0 - 10.0 x ULN if	>10.0 x ULN if
		baseline was	baseline was	baseline was	baseline was
		normal;	normal;	normal;	normal;

Laboratory	CTCAE Term	Grade 1	Grade 2	Grade 3	Grade 4
		> 1.0 - 1.5 x baseline if baseline was abnormal	>1.5 - 3.0 x baseline if baseline was abnormal	>3.0 - 10.0 x baseline if baseline was abnormal	>10.0 x baseline if baseline was abnormal
	Alkaline phosphatase increased	>ULN - 2.5 x ULN if baseline was normal;	>2.5 - 5.0 x ULN if baseline was normal;	>5.0 - 20.0 x ULN if baseline was normal;	>20.0 x ULN if baseline was normal;
		2.0 - 2.5 x baseline if baseline was abnormal	>2.5 - 5.0 x baseline if baseline was abnormal	>5.0 - 20.0 x baseline if baseline was abnormal	>20.0 x baseline if baseline was abnormal
	Creatinine increased	>ULN - 1.5 x ULN	>1.5 - 3.0 x baseline; >1.5 - 3.0 x ULN	>3.0 x baseline; >3.0 - 6.0 x ULN	>6.0 x ULN
	CPK increased	>ULN - 2.5 x ULN	>2.5 x ULN - 5 x ULN	>5 x ULN - 10 x ULN	>10 x ULN
	Hyperkalemia	Potassium	Potassium	Potassium	Potassium
		>ULN - 5.5 mmol/L	>5.5 - 6.0 mmol/L	>6.0 - 7.0 mmol/L	>7.0 mmol/L
	Serum amylase increased	>ULN - 1.5 x ULN	>1.5 - 2.0 x ULN	>2.0 - 5.0 x ULN	>5.0 x ULN
	Hypoglycemia	Glucose	Glucose	Glucose	Glucose
		<lln -="" 55="" dl;
<lln -="" 3.0="" l<="" mmol="" td=""><55 - 40 mg/dL; <3.0 - 2.2 mmol/L	<40 - 30 mg/dL; <2.2 - 1.7 mmol/L	<30 mg/dL; <1.7 mmol/L;	</lln></lln>	<55 - 40 mg/dL; <3.0 - 2.2 mmol/L	<40 - 30 mg/dL; <2.2 - 1.7 mmol/L	<30 mg/dL; <1.7 mmol/L;
	GGT increased	>ULN - 2.5 x ULN if baseline was normal;	>2.5 - 5.0 x ULN if baseline was normal;	>5.0 - 20.0 x ULN if baseline was normal;	>20.0 x ULN if baseline was normal;
		2.0 - 2.5 x baseline if baseline was abnormal	>2.5 - 5.0 x baseline if baseline was abnormal	>5.0 - 20.0 x baseline if baseline was abnormal	>20.0 x baseline if baseline was abnormal
Hematology	Anemia	Hemoglobin (Hgb)	Hemoglobin (Hgb)	Hemoglobin (Hgb)	
		<lln -="" 10.0="" dl;
<lln -="" 6.2="" l;
<lln -="" 100="" g="" l<="" td=""><10.0 - 8.0 g/dL; <6.2 - 4.9 mmol/L; <100 - 80 g/L	<8.0 g/dL; <4.9 mmol/L; <80 g/L		</lln></lln></lln>	<10.0 - 8.0 g/dL; <6.2 - 4.9 mmol/L; <100 - 80 g/L	<8.0 g/dL; <4.9 mmol/L; <80 g/L	
	Hemoglobin increased	Hemoglobin > ULN &	Hemoglobin > ULN &	Hemoglobin > ULN &	
		Increase in >0 - 2 g/dL	Increase in >2 - 4 g/dL	Increase in >4 g/dL	
	CD4 lymphocytes decreased	<lln -="" 500="" mm3;
<lln -="" 0.5="" 10e9="" l<="" td="" x=""><500 - 200/mm3; <0.5 - 0.2 x 10e9 /L	<200 - 50/mm3; <0.2 x 0.05 - 10e9 /L	<50/mm3; <0.05 x 10e9 /L	</lln></lln>	<500 - 200/mm3; <0.5 - 0.2 x 10e9 /L	<200 - 50/mm3; <0.2 x 0.05 - 10e9 /L	<50/mm3; <0.05 x 10e9 /L
	Neutrophil count decreased	<lln -="" 1500="" mm3;
<lln -="" 1.5="" 10e9="" l<="" td="" x=""><1500 - 1000/mm3; <1.5 - 1.0 x 10e9 /L	<1000 - 500/mm3; <1.0 - 0.5 x 10e9 /L	<500/mm3; <0.5 x 10e9 /L	</lln></lln>	<1500 - 1000/mm3; <1.5 - 1.0 x 10e9 /L	<1000 - 500/mm3; <1.0 - 0.5 x 10e9 /L	<500/mm3; <0.5 x 10e9 /L
	White blood cell decreased	<lln -="" 3000="" mm3;
<lln -="" 10e9="" 3.0="" l<="" td="" x=""><3000 - 2000/mm3; <3.0 - 2.0 x 10e9 /L	<2000 - 1000/mm3; <2.0 - 1.0 x 10e9 /L	<1000/mm3; <1.0 x 10e9 /L	</lln></lln>	<3000 - 2000/mm3; <3.0 - 2.0 x 10e9 /L	<2000 - 1000/mm3; <2.0 - 1.0 x 10e9 /L	<1000/mm3; <1.0 x 10e9 /L
	Platelet count decreased	<lln -="" 75,000="" mm3;
<lln -="" 10e9
/L</lln></lln>	<75,000 - 50,000/mm3; <75.0 - 50.0 x 10e9 /L	<50,000 - 25,000/mm3; <50.0 - 25.0 x 10e9 /L	<25,000/mm3; <25.0 x 10e9 /L
Coagulation	INR increased	>1.2 - 1.5;	>1.5 - 2.5;	>2.5;	
		>1 - 1.5 x baseline if on anticoagulation	>1.5 - 2.5 x baseline if on anticoagulation	>2.5 x baseline if on anticoagulation	
		•	•	•	•

For the other parameters, the incidence of abnormalities (as defined by normal ranges) prior to the first dose of study drug and after the first dose of study drug will be summarized with counts and percentages of subjects.

The incidence of treatment-emergent laboratory abnormalities, defined as values that increase at least one toxicity grade from baseline at any time post baseline up to and including the date of last dose of study drugs plus 30 days, will be summarized with counts and percentages of subjects by treatment group. If baseline data are missing, then any graded abnormality (i.e., at least a Grade 1) will be considered treatment-emergent. If no pre-treatment laboratory value is available, the baseline value will be assumed to be normal (i.e., no grade [Grade 0]) for the summary of graded laboratory abnormalities.

Evaluation of drug-induced serious hepatotoxicity (eDISH) plot will be provided to display peak serum ALT and Total Bilirubin (TB) levels for each subject. The peak serum AST versus TB levels for each subject will also be provided.

